6.5.14 Imaging

Chest X-rays (PA and lateral) will be performed at Baseline and post-procedure in accordance with the IFU. These will be documented in the appropriate eCRF, subject-identifying information redacted, and submitted to Boston Scientific Corporation upon request.

HRCT will be performed at the Baseline Visit and 12 and 36 month Follow-up Visits. HRCT will include both inspiratory and expiratory scans completed per the recommendations provided as part of the PneumRx QCT service.

7 ADVERSE EVENTS

7.1 Adverse Event Definitions

An adverse event (AE) is any untoward medical occurrence, unintended disease or injury, or untoward clinical signs (including abnormal laboratory findings) in a study subject, user or other persons whether or not related to the investigational medical device.

Adverse experience will be considered synonymous with the term AE and vice versa.

7.1.1 Definitions of SAE/SADE/USADE/Device Deficiency

Serious Adverse Event (SAE)

An SAE is any untoward medical occurrence that:

- results in death;
- Led to serious deterioration in the health of the subject , that either resulted in
 - A life-threatening illness or injury, or
 - A permanent impairment of a body structure or a body function, or
 - In-patient or prolonged hospitalization, or
 - Medical or surgical intervention to prevent life-threatening illness or injury or permanent impairment to a body structure or a body function
- Led to fetal distress, fetal death or a congenital anomaly/birth defect.

Serious Adverse Device Effect (SADE)

An SADE is an adverse effect that has resulted in any of the consequences characteristic of a serious adverse event.

Unanticipated Serious Adverse Device Effect (USADE)

A USADE is a serious adverse device effect which by its nature, incidence, severity or outcome has not been identified in the current version of the risk analysis report

Device Deficiency

A device deficiency is an inadequacy of a medical device with respect to its identity, quality, durability, reliability, safety or performance. Device deficiencies include malfunctions, use errors and inadequate labeling.

A device malfunction is the failure of a medical device to perform in accordance with its intended purpose when used in accordance with the instructions for use.

⋮
SAE information will be collected throughout the study. SAEs will be recorded on the eCRF by the investigator or authorized designee. Event, date of onset, duration, serious/non-serious, anticipated/not anticipated, severity, relationship to the procedure/device, outcome, and action taken will be recorded. Additional information on specific events may be requested in the eCRFs. All events must be recorded in English. Any source documentation required to investigate SAEs for reporting must be translated to English.

NOTE: A planned hospitalization for a pre-existing condition, or a procedure required by the clinical protocol, without a serious deterioration in health, is not considered to be a SAE.

An anticipated SAE is any SAE, the nature or severity of which is identified in the IFU. Any other device related SAE will be considered an unanticipated adverse device effect (USADE).

All SAEs that are determined to be related to the device or procedure will be evaluated for reportability in accordance with MEDDEV 2.7/3 revision 3. The investigator will be responsible for submitting source documentation to PneumRx in order to document the investigation for the event.

7.2 Recording Adverse Events (AE)

Subjects will be required to report AEs of interest. At each study visit, site staff will ask general, open-ended, non-directed questions to obtain information about AEs. If the subject is unable to attend a trial visit, AEs can be collected by telephone contact. At any time during the study, the Subject may volunteer information that meets the definition of an AE.

The investigator should record all SAEs and specific Respiratory AEs of interest in the eCRFs. Below is a list of specific Respiratory AEs of interest that should be recorded:

- COPD Exacerbation
- Hemoptysis
- Pneumothorax
- Lower Respiratory Tract Infection/Pneumonia
- Tissue Reaction, Localized (a.k.a. Coil Associated Inflammatory response syndrome (CAIRs), also called Coil Associated Opacity (CAO) in the IFU)

Investigators will obtain all the information required to complete the AE form. Where possible, a diagnosis, rather than a list of signs or symptoms, should be recorded. Any medical management of an event and the resolution of an event must be recorded in source documentation and on the appropriate eCRF using medical terminology according to sponsor instructions.

For each SAE and specific respiratory AEs of interest, the following information will be recorded at a minimum:

- AE term
- Serious/non-serious
- Severity
- Action taken
- Relationship to Coil System
- Expected/Unexpected
- Date and time of onset
- Date and time of resolution

Was the subject withdrawn from the study due to the AE

Any SAE experienced by a subject will be followed until the SAE has resolved to the PI's or sub-investigator's satisfaction or is considered stable. If a problem still exists, then the PI or sub-investigator at his/her discretion will ask the subject to come back to the clinic for further evaluation. SAEs should be managed as discussed in Section 7.5.

7.3 Recording and Reporting Device Deficiencies

All device deficiencies must be reported to BSC within 24 hours of becoming aware of the event. The report should be submitted in English with all available information. Devices should be returned to Boston Scientific Corporation via the standard commercial method.

7.4 Device and Procedure Causality Assessment

The PI or sub-investigator must indicate whether he/she believes the SAE is unrelated, possibly related (reasonable possibility that the investigational device and/or procedure caused the SAE) or probably related to the medical device or procedure.

7.5 Submitting Expedited Safety Reports

All SAEs and UADEs (defined above) must be reported to the sponsor via EDC within 24 hours of learning of the event. Any supporting source documents required to investigate the SAE or USADE must be provided as soon as possible to PneumRx.

The sponsor must promptly inform the Independent Ethics Committee (IEC), both CPP and ANSM in France, of all USADEs and SAEs as required per site IEC requirements. These events will be reported by the sponsor, as appropriate, to the regulatory authorities according to relevant jurisdictional medical device regulations. As the Coil System is a CE marked and commercially available device in the EU, Medical Device Vigilance System reporting requirements are applicable to adverse incidents reported through this study.

7.6 Periodic Safety Reporting

Periodic annual safety reports will be submitted to the ANSM and will be communicated across all study centers.

7.7 Expected Adverse Events

AEs reported through clinical studies and post-market vigilance (in the EU and OUS regions) are detailed in the IFU. AEs which may be observed with endobronchial devices, systems for placement of these devices, and related procedures (including diagnostics and bronchoscopy procedures) and use of the Coil System include, but are not limited to, the events shown below. These events may vary in frequency and severity.

- Allergic Reaction
- Emphysema, Subcutaneous
- Pneumonia*
- Aspiration
- Hemoptysis, including Severe Hemoptysis
- Pneumonitis
- Bleeding or Hemorrhage
- Hoarseness
- Pneumothorax
- Bronchial Blood Clot
- Hypertension
- Procedure-Related Complication (e.g., fever, spasm)
- Bronchial Ulceration
- Hypotension
- Pulmonary Embolism

- Bronchospasm
- Cardiac Arrhythmias
- COPD Exacerbation
- Cough
- Death
- Device Dislocation
- Dyspnea
- Infection
- Inflammation
- Lung Abscess
- Pain
- Painful Respiration
- Pleural Effusion
- Pleural Fistula
- Respiratory Distress
- Respiratory Failure
- Respiratory Tract Infection
- Sedation – Related Complications (e.g., nausea, vomiting, headache)
- Sepsis
- Tissue Reaction, Localized (a.k.a CAIRs/CAO)
- Tissue Trauma, Procedural (e.g., tissue perforation, dissection)

*A recognized, non-infectious localized tissue reaction, also termed Coil Associated Inflammatory response syndrome (CAIRs), also called Coil Associated Opacity (CAO) in the IFU, may occur in the area of implanted coils and is typically diagnosed on imaging (chest X-ray or CT scan). This is believed to be an inflammatory response that presents with pneumonia-like symptoms, including chest or pleuritic pain/discomfort, increased dyspnea, fatigue, and/or haze or infiltrates on chest X-ray, and may be difficult to distinguish from pneumonia. While some degree of CAIRs/CAO has been observed in clinical trials up to 2 months following the Coil procedure, many of these events are asymptomatic or symptomatically mild, resolve with limited intervention, and do not develop into serious adverse events (SAEs). However, CAIRs/CAO can become severe and require prompt and specific intervention. Thus, subjects are advised to contact their treating physician immediately for follow-up if they experience pneumonia-like symptoms.

Note: Additional interventional procedures may be necessary if subjects experience some of these potential AE(s) following Coil treatment.

8 STATISTICAL CONSIDERATIONS

8.1 Trial Design and Determination of Sample Size

A total of 120 Subjects were randomized in a 2:1 ratio of Treatment to Control respectively (80 treatment group subjects, 40 Control group subjects).

8.2 Statistical Analysis

The statistical analysis plan (SAP) will be a separate document and will be updated as required, in association with any protocol amendments. The plan will include detailed descriptions of analysis methods, tables, listings and figures and will describe statistical programming considerations.

8.3 Analysis Populations and Sub-Groups

Intent to Treat Population (ITT) – All randomized Subjects, regardless of whether or not treatment was attempted.

Per Protocol Population (PP) - All randomized Subjects without major protocol deviations (see Section 10.9).

Safety Population - All randomized Subjects who enter the bronchoscopy suite for the initial Coil procedure.

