	
Death, Led to serious deterioration in the health of the subject that either resulted in A life threatening illness or injury, or A permanent impairment of a body structure or a body function, or In-patient or prolonged hospitalization, or Medical or surgical intervention to prevent life-threatening illness or injury or permanent impairment to a body structure or a body function Led to fetal distress, fetal death or a congenital anomaly/birth defect.
 
Information on Specific Respiratory Events of interest will be collected and analyzed via event specific case report forms. These events of interest include:
 
 • COPD exacerbation • Hemoptysis • Pneumothorax • Lower Respiratory Tract Infection/Pneumonia • Tissue Reaction, Localized (a.k.a. Coil Associated Inflammatory Response Syndrome (CAIRS), also called Coil Associated Opacity (CAO) in the IFU)

Statistical Analyses:
	
The co-primary effectiveness endpoint will be analyzed on the intent-to-treat (ITT) population through the 6-month visit, using descriptive statistics to summarize results separately for treatment and control groups. No comparative inferential statistics will be conducted.

	
Safety analyses will be conducted on the safety population defined as those subjects who enter the bronchoscopy suit for the initial Coil

--	--

	
procedure. AE and SAEs will be summarized by Treatment group based on MedDRA codes. Incidence rates through 6 months will be summarized for treatment and control groups. Events will also be summarized by relevant, discrete time periods including the Treatment recovery period (30 days from either treatment).
 
Descriptive statistics will summarize percent change in FEV₁ as well as AEs and SAEs at 12 and 36 months follow-up for all coil treated subjects.

RESULTS	

Number of subjects to be analyzed
	
A total of 120 Subjects were randomized in a 2:1 ratio of Treatment to Control, respectively (80 Treatment group subjects, 40 Control group subjects).

Duration of the follow-up	Subjects will continue in the study through 36 months from first Coil implant. If Control subjects don't participate to crossover, they will exit the study immediately.
----------------------------------	--

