4.3 Subject Crossover

Control group Subjects will be eligible for crossover to Treatment as soon as possible. Control subjects will be eligible for crossover if they still meet all inclusion and exclusion criteria, and if the patient is deemed to benefit from the Coil treatment by the investigator, based on best medical judgment. Crossover subjects will continue in the study through 36 months from first Coil implant. If Control subjects do not crossover to treatment, they will exit the study immediately.

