6.4.4 Patient completion or early withdrawal

Subjects who receive the Treatment procedure complete the study 36 months after the initial implant procedure or when they choose to withdraw from the study, if earlier than 36 months post-procedure. In the event of a continuing SAE related to the Coil system, the subject will be asked to return for follow-up until the SAE has resolved or is deemed to be continuing indefinitely. Control subjects who do not crossover to treatment will exit the study immediately.

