8.6 Safety Analyses

Safety analyses will be conducted on the safety population defined as those Subjects who enter the bronchoscopy suite for the initial Coil procedure. AE and SAEs will be summarized by treatment group based on MedDRA codes. Incidence rates through 6 months will be summarized for treatment and control groups. For coil treated subjects, events will also be summarized by relevant, discrete time periods including the Treatment recovery period (30 days from either treatment), as well as through the 12- and 36-month follow-up periods.

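### The Safety Population is defined by entry to the suite for a Coil procedure, so the planned 6-month Control safety summary has either no subjects or only Controls who later cross over

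*Combined protocol and SAP*

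**What the plan says.** Section 8.3 defines the set: "Safety Population - All randomized Subjects who enter the bronchoscopy suite for the initial Coil procedure". Section 8.6 applies it to everything that follows: "Safety analyses will be conducted on the safety population defined as those Subjects who enter the bronchoscopy suite for the initial Coil procedure". The Statistical Analyses row of the synopsis repeats the restriction ("defined as those subjects who enter the bronchoscopy suit for the initial Coil" procedure).

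Section 8.6 then plans a comparison by group: "Incidence rates through 6 months will be summarized for treatment and control groups". The synopsis plans the same. A further sentence in Section 8.6 treats the device summaries as an addition: "For coil treated subjects, events will also be summarized by relevant, discrete time periods".

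Controls reach the suite only through crossover, which is conditional. Section 4.3 says: "Control subjects will be eligible for crossover if they still meet all inclusion and exclusion criteria, and if the patient is deemed to benefit", the benefit being judged by the investigator. For the rest it says: "If Control subjects do not crossover to treatment, they will exit the study immediately". Section 6.4.4 agrees ("Control subjects who do not crossover to treatment will exit the study immediately"), as does Section 5.1.4.

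Section 8.3 also defines an intent-to-treat set of all randomized subjects, but Section 8.5 uses it for effectiveness only. No other safety set is defined for Controls. No time origin is given for the 6-month incidence in either group.

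**The concern.** Safety is part of the primary objective (Section 3.1.1), and the 6-month by-group table is where events after Coil treatment are set beside events under medical management. For that comparison the Control column should describe the 40 subjects randomized to Control. The stated set instead admits a Control only after something that happens after randomization and depends on how the subject has fared.

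The link to outcome is plausible. COPD exacerbation is a respiratory event of interest in Section 7.2. Exclusion criterion 9 in Section 4.2.2, which concerns recent exacerbations, must be met again at crossover. An event that the table should count can therefore help to keep the subject out of the table. Treatment subjects who never reach the suite are dropped too. Their first procedure is due within 45 days of baseline (Section 5.1.3), whereas one of the protocol's crossover statements has Controls wait 6 months.

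**Working it through.** **1. The plan's own figure.** 120 randomized 2:1 gives 120 × 2/3 = 80 Treatment and 120 × 1/3 = 40 Control, as in Section 8.1. No event rate, crossover proportion or dropout rate is given, so every rate below is an assumption. The examples in steps 3 to 5 are separate and do not share one timeline.

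**2. Each kind of Control under the stated set.**

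| Control subject | Enters the suite? | In the Safety Population? |
|---|---|---|
| Crosses over | Yes, later | Yes |
| Declines, is ineligible or is not judged to benefit | No, exits | No |
| Withdraws before crossover | No | No |
| Dies before crossover | No | No |

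Two literal readings follow. (a) If the Control column means subjects who entered the suite while still under medical management, it has 0 of 40 subjects and there is no rate to report. (b) If it means Controls who later cross over, the denominator is 40 minus all those in the last three rows.

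**3. Deaths under reading (b).** With d deaths before crossover, the table shows 0 whatever d is; over all randomized Controls the proportion is d/40.
- d = 1: 1/40 = 2.5% (exact 95% interval 0.1% to 13.2%).
- d = 2: 2/40 = 5.0% (0.6% to 16.9%).

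Full crossover of the survivors does not restore these. Suppose 2 deaths and serious events in 25% of the 38 survivors (9.5 expected). If all survivors cross over, the table shows no deaths and 9.5/38 = 25.0% with a serious event, against (9.5 + 2)/40 = 28.75% over all 40.

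**4. Other events under reading (b).** Suppose 8 of 40 Controls (20.0%) have an event before crossover, 28 of the 32 without one cross over, and k of the 8 cross over. The reported rate is k/(28 + k).

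| k | Reported rate | Against 20.0% |
|---|---|---|
| 0 | 0/28 = 0.0% | too low |
| 2 | 2/30 = 6.7% | too low |
| 4 | 4/32 = 12.5% | too low |
| 7 | 7/35 = 20.0% | unbiased |
| 8 | 8/36 = 22.2% | too high |

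The turning point is equal crossover: 7/8 = 28/32 = 87.5%. The Control rate is understated only if Controls with events cross over less often than those without.

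**5. Changing the denominator alone is not enough.** If Control observation ends early, a crude proportion over all 40 falls short of the 6-month risk. With 6-month risk p and constant hazard, the proportion by t months is 1 − (1 − p)^(t/6). For p = 0.20 this is 3.7%, 7.2% and 10.6% at 1, 2 and 3 months, against 20.0% at 6. For p = 0.10 it is 1.7%, 3.5% and 5.1%; for p = 0.30 it is 5.8%, 11.2% and 16.3%.

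A person-time rate removes this under constant hazard: at p = 0.20 it is 3.72 first events per 100 person-months at every t. The Coil arm is unlikely to have a constant hazard. Section 8.6 singles out a 30-day recovery period after each treatment, and Section 7.7 describes tissue reactions up to 2 months after the procedure. A 6-month Coil rate beside a 1 to 3 month Control rate could dilute early Coil harm.

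**The case against.** **Intent.** The sentence adding summaries for Coil-treated subjects suggests that the by-group table was meant to hold a medical-management column. That is probably right, but the stated set does not deliver it, and Section 8.3 shows that all-randomized wording was at hand.

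**The separate SAP.** Section 8.2 leaves detailed methods to another document. None of its text on safety sets is among the documents supplied, and it could cure the problem only by departing from Sections 8.3 and 8.6 and the synopsis.

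**Events are not lost.** This stands. Serious events, including deaths, are collected throughout (Section 7.1.1) and go to the sponsor within 24 hours (Section 7.5). A reader might infer that Control deaths vanish from the trial's safety record; the documents do not support that.

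**Bias is not certain.** This also stands. A reader might infer that the plan builds in a spurious excess of deaths on Coil. Under reading (a) there is no Control rate, so no excess can be shown. Under reading (b) its size would also depend on how many Treatment deaths follow suite entry. Nor does the text show that the omitted Controls are always those who did worst: step 4 contains an unbiased and a reversed case. Criterion 9 is narrower than a bar on any exacerbation. A single event more than 3 months earlier, or a recent one that does not call for assessment for hospital admission, does not exclude by itself. Hemoptysis, pneumothorax or pneumonia exclude only if they leave an excluding condition. If crossover is immediate, less is lost before it.

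**No test depends on this.** True: the analysis is descriptive. That limits the consequence but does not make the table interpretable.

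**Conclusion.** The point holds as a defect in the stated analysis set. Followed literally, the 6-month Control safety column is empty or confined to Controls who later cross over. This rests on the text alone.

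The consequences are conditional. If later crossovers are tabulated as Control, deaths before crossover show as 0 whatever their number. For other events understatement is plausible, because the exacerbation exclusion is re-applied, but neither its direction nor its size can be fixed from the documents. The percentages above illustrate the mechanism and do not estimate the bias. The matter should be corrected before the safety tables are produced; it does not threaten a hypothesis test or the reporting of individual events.

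**What to change.** In Sections 8.3 and 8.6 and the synopsis:
- Keep the suite-entry set for summaries of Coil-exposed subjects only.
- For the by-group 6-month summary, use all randomized subjects as assigned (80 and 40, the intent-to-treat set already defined), with randomization as time zero in both arms.
- End Control observation at the earliest of month 6, suite entry for crossover, study exit or death. End Treatment observation at the earliest of month 6, exit or death.
- Use a time-to-event estimate or compare the arms over matched windows, not a crude person-time rate alone.
- Report how many in each arm died, exited or crossed over by month 6. Leaving by crossover depends on the subject's condition, so the reader needs these counts to judge the estimate.
- Show post-crossover events in a separate column as Coil exposure.

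The statements on crossover timing must be reconciled, because they determine how long Controls are observed. The synopsis and Section 3.2 each give both a 6-month wait and crossover without delay; Section 4.3 gives the latter, and Section 5.1.4 gives immediate treatment.

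State one limitation. The Section 1 schedule shows no adverse event contact for Controls between randomization and crossover. The synopsis and Section 7.2 do allow ongoing, volunteered and telephone collection, but non-serious Control events may be under-captured, and new tables cannot repair that.

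The cost is a wording amendment, which under Section 10.7 needs investigator and sponsor approval and ethics submission, a matching change to the separate SAP, and modest extra tabulation. Timing from randomization adds some unexposed time to the Treatment arm before its first procedure; the retained Coil-exposed summaries cover the period after it. No new visits or data are required.
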